### 2.3 Other Efficacy Endpoints

- PGIC at Weeks 4 and 12
- Change from baseline to Weeks 4 and 12 in the Pittsburgh Sleep Quality Index (PSQI) total score
- Change from baseline to Weeks 4 and 12 in the total score and 4 domain scores of Menopause-Specific Quality of Life (MENQOL)
- Change from baseline to Weeks 4 and 12 in the domain scores of 36-Item Short Form Health Survey (SF-36)

- Change from baseline in the average daily severity score of moderate to severe VMS at Weeks 4 and 12, defined as  $2 \times F_{mo} + 3 \times F_{se}$

## 2.4 Safety Assessments

### 2.4.1 Adverse events (AEs)

An AE is any untoward medical occurrence in a subject or clinical investigation subject administered a pharmaceutical product that does not necessarily have a causal relationship with this treatment.

AEs will be coded using Medical Dictionary for Regulatory Activities (MedDRA) central coding dictionary, Version 20.0 or the later (to be updated at final version).

Treatment-emergent AEs (TEAEs) are defined as AEs that started or worsened in severity on or after the first dose of double-blind study medication. The treatment relationship with the AE is in 2 categories (reasonable possibility, no reasonable possibility). The detail is included in protocol.

### 2.4.2 Physical examination

The complete physical examination consists of a routine assessment of major body systems: abdominal, cardiovascular, general appearance, head, eyes, ears/nose/throat, lymph nodes, musculoskeletal, neck, neurological, dermatological, respiratory, and 'other'.

The routine physical examination consists of a routine assessment of the following body systems: abdominal, cardiovascular, general appearance, respiratory, and 'other'.

The complete physical examination is performed at Screening. The routine physical examination is performed at run-in period and Visits 3 to 7.

### 2.4.3 Breast examination

The breast examination consists of symmetry of breast shape, contour of breast, appearance of skin, nipple, areola, lymph nodes status, presence and characterization of lesions. The breast examination is performed at Screening, Visits 3 and 7.

### 2.4.4 Vital signs

- Sitting Systolic Blood Pressure (mmHg)
- Sitting Diastolic Blood Pressure (mmHg)
- Sitting Pulse Rate (bpm)
- Tympanic Body Temperature (°C)
- Body Weight (kg)

### 2.4.5 ECG parameters

- Heart rate (bpm)
- PR (msec)

- RR (msec)
- QRS (msec)
- QT (msec)
- QTcF (msec)
- QTcB (msec)

#### 2.4.6 Clinical laboratory assessments

The clinical lab tests are listed in the Table 2.

**Table 2 Routine Laboratory Tests**

Hematology:	
Hemoglobin	Mean corpuscular hemoglobin
Hematocrit	Mean corpuscular hemoglobin concentration
Platelet count	Mean corpuscular volume
Red blood cell count	White blood cell count and differential
Biochemistry:	
Alkaline phosphatase	Cholesterol
Aspartate aminotransferase	Triglycerides
Alanine aminotransferase	High density lipoprotein-cholesterol
Gamma-glutamyl transpeptidase	Low density lipoprotein-cholesterol
Potassium	Protein (total)
Sodium	Albumin
Chloride	Creatine kinase
Inorganic phosphate	Creatinine
Glucose	
Urea	
Bilirubin (direct and total)	
Coagulation:	
Prothrombin time	Activated partial thromboplastin time
International normalized ratio	
Urinalysis:	
Specific gravity, pH, protein, glucose, ketones, urobilinogen, blood	
Microscopic examination 	

 Performed only if required, based on urinalysis results.

#### 2.4.7 Reproductive hormones

- Luteinizing hormone (LH)
- Follicle stimulating hormone (FSH)
- Estradiol (E2)

#### 2.4.8 Endometrial safety

- Endometrial thickness, as measured by transvaginal ultrasound
- Incidence of endometrial hyperplasia, as measured by endometrial biopsy

#### **2.4.9 Depression and Anxiety**

Depression as measured by 8-Item Patient Health Questionnaire (PHQ-8). The total scores of PHQ-8 will be used as the safety endpoint.

Anxiety as measured by the 7-item Generalized Anxiety Disorder questionnaire (GAD7). The total scores of GAD7 will be used as the safety endpoint.

#### **2.5 Pharmacokinetics (PK) Evaluations**

MT-8554 concentrations in plasma will be measured at 5 visits during the Double-blind Treatment period. Planned time points for pharmacokinetics (PK) evaluation are as follows: Visit 3 (Day 1), Visit 4 (Week 2), Visit 5 (Week 4), Visit 6 (Week 8) and Visit 7 (Week 12).

Population PK analysis will be performed using the plasma concentrations of MT-8554 obtained in this study alone and/or in combination with data obtained from other clinical studies. Details of the population PK analysis will be presented in a modelling plan. Population PK analysis results will be reported separately from the clinical study report.

#### **2.6 Demographic and Other**

##### **2.6.1 Demographic and Baseline Characteristic**

The following subject demographic and baseline characteristic are collected.

- Age (years)
- Sex
- Race
- Ethnicity
- Weight (kg)
- Height (cm)
- BMI (kg/m^2)
- Menopausal status
- Antidepressant use
- Diabetic status
- Cardiovascular history
- Hypertension
- Heart Failure
- Baseline labs (creatinine, the estimated glomerular filtration rate [eGFR], haematocrit)
- Average daily VMS frequency
- Average daily VMS severity

## 2.6.2 Medical History

The subjects Medical and surgical history will be collected and recorded in the clinical database.

## 2.6.3 Prior or Concomitant Medications

Prior medications are defined as any medication taken prior to the double-blind treatment period. Any prior medication, including prescription and over-the-counter medications, taken within 1 month prior to Screening will be collected.

Concomitant medication is defined as any medication, other than study medication, which is taken on or after the start day of double blind treatment.

The prior and concomitant medication data will be coded using World Health Organization Drug Dictionary (WHO Herbal Dictionary).

## 3. PLANNED ANALYSES

Detail of what Listing, Table and Figure will be created at each analysis term is described in Section 11 List of Listings, Tables and Figures.

### 3.1 Data Monitoring Committee (DMC)

An independent DMC, composed of experts in the management of subjects with the disease under study will be established for MT-8554-A01 according US FDA guidance. An independent biostatistician will be assigned to the DMC to maintain the integrity of the study blind and provide safety data at regular predefined intervals during the study and provide the interim analysis to the DMC.

The primary purpose of this committee will be to review safety data for the protection of subject safety. In addition the DMC will review efficacy data for the interim analysis and make recommendations to the Sponsor. When approximately 50% of subjects complete the Week 12 visit, the planned interim analysis will be conducted to determine whether the study will be stopped due to futility, safety concerns, or both.

[figure not shown]
A DMC charter will outline the scope and key responsibilities, timing of reviews, communications between the DMC and the Sponsor, and recommendations and action rules for the study.

### 3.2 Interim Analyses

In addition to on-going safety monitoring, there will be one planned interim assessment for safety and one planned interim analysis for efficacy (futility) and safety.

**3.2.1 Interim Safety assessment**

A large rectangular area of the page is completely blacked out, indicating that the content for the 'Interim Safety assessment' section has been redacted.

**3.2.2 Interim Analysis for Safety and efficacy**

A large rectangular area of the page is completely blacked out, indicating that the content for the 'Interim Analysis for Safety and efficacy' section has been redacted.

Then DMC will evaluate the interim analysis results. The DMC will review the data and provide recommendations for the study to the Sponsor.

A large rectangular area of the page is completely blacked out, indicating that the content following the paragraph about the DMC's role has been redacted.

### **3.3 Final Analysis**

The final analysis will be conducted with unblinded data after database lock.

All the planned efficacy and safety analyses in this SAP will be performed by [REDACTED]

### **3.4 Other Analysis**

There is no plan for analyses other than what is defined in this SAP.

## **4. ANALYSIS POPULATION(S)**

### **4.1 Randomized Population**

Randomized Population includes all subjects who are randomized, regardless of whether they receive any study drug. Data from the all randomized subjects analysis set will be analyzed by the treatment group assigned at the time of randomization, even if the subject does not receive the correct treatment, is not compliant with the protocol or does not follow through with the study until completion.

### **4.2 Safety (SAF) Population**

Safety (SAF) Population includes all randomized subjects who received at least 1 dose of study medication. The safety population will be used for all safety analyses. The subject exact treatment received will be used for safety analyses.

#### 4.3 Intent-to-treat (ITT) population

Intent-to-treat (ITT) population: includes all randomized subjects who have at least 1 post-baseline value for primary efficacy endpoint. The ITT population will be used for all efficacy analyses. The subject randomized treatment will be used for efficacy analyses.

#### 4.4 Per-protocol (PP) population

Per-protocol (PP) population: includes all ITT subjects who do not have any major protocol deviations. The PP population will be used for primary efficacy analyses as well. The subject randomized treatment will be used for efficacy analyses.

#### 4.5 Pharmacokinetic (PK) population

PK population includes all randomized subjects who receive at least 1 dose of MT-8554 and who have at least 1 post-dose value for plasma concentration without important protocol deviations which may affect the PK of MT-8554.

### 5. GENERAL CONSIDERATIONS

The statistical evaluation will be performed using SAS® Version 9.4 or later.

Efficacy summaries will be performed on the ITT. As part of sensitivity analysis will be performed on the PP population. Safety summaries will be performed on the SAF. PK summaries will be performed on the PK population.

#### 5.1 Number of digits to report

**Table 3 Number of decimal places (DP) or significant digits (SD)**

Statistic	Specification	Apply to
Minimum, maximum	same number of DPs as the data provided in the datasets	All original, i.e. non-derived, data provided in the datasets
mean, median, , confidence intervals, lsmean	one more DP than the raw data	All
SD, SE	two more DP than the raw data	All
Percentages	1 DP	All
p-values	3 DP	All
Odds Ratio	2DP	All
Hazard Ratio	3DP	All

#### 5.2 Significance level and confidence interval

The statistical tests will be performed as two-sided with significance level of 5%. The confidence intervals will be determined with a confidence level of 95%.

### 5.3 Descriptive statistics values to calculate

Where appropriate, variables will be summarized descriptively (frequency and percent will be summarized for categorical variables; mean, standard deviation [SD], median, minimum, and maximum will be presented for continuous variables) by study visit and by treatment group.

The denominator for the percentages will be the total number of subjects in the treatment group and Analysis Set being presented, unless otherwise specified (e.g. on some occasions, percentages maybe calculated out of the total number of subjects with available data at a particular visit and/or time point).

Summary statistics required for PK or related data are described in relevant sections later.

### 5.4 Derived variables

The subjects' diary data will be used to derive the primary and some secondary efficacy endpoints. Subjects can use paper diary as contingent back up when they have problem with their ediary device. The paper diary data will be used only for the days that subjects have paper diary without ediary data. This means the paper diary data is not used when ediary data is available.

#### 5.4.1 Definition of the average daily frequency of moderate to severe VMS

The average daily frequency of moderate to severe VMS at a time point (Baseline, Week 1, 2, 3, 4, ..., 12) is the average of the frequency of moderate to severe VMS of available diary days in a 7-day window. It will be rounded off the second decimal place and reported the value to the first decimal place. The nominal day for each time point relative to the first dose day will be used. The analysis windows are defined in the table below. The other efficacy endpoints based on average daily VMS diary data will be derived using these windows accordingly.

**Table 4 Analysis visit windows of diary days used for average daily frequency of moderate to severe VMS**

	Nominal day	Window
Baseline		Day -7 to -1
Week 1	8	Day 2 to 8
Week 2	15	Day 9 to 15
Week 3	22	Day 16 to 22
Week 4	29	Day 23 to 29
Week 5	36	Day 30 to 36
Week 6	43	Day 37 to 43
Week 7	50	Day 44 to 50
Week 8	57	Day 51 to 57
Week 9	64	Day 58 to 64
Week 10	71	Day 65 to 71
Week 11	78	Day 72 to 78
Week 12	85	Day 79 to 88

VMS data on the day of Week 12 visit is not used for the calculation of average daily VMS frequency.

If the count of available VMS data in a specific week is less than four (4), the latest diaries in the previous window can be carried as needed to make 4 diaries available in this window. Then the average daily VMS frequency in the week is calculated.

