2.2 Study endpoints

2.2.1 Co-primary efficacy endpoints

- Change from baseline in the average daily frequency of moderate to severe VMS, defined as the sum of the number of moderate to severe VMS during 1 week divided by the number of days with data. The daily score here and below are average scores from a 7-day period. Details will be defined in the Statistical Analysis Plan (SAP).
- Change from baseline in the average daily severity score of mild to severe VMS. Baseline VMS severity score is defined as $(2xFmo + 3xFse)/(Fmo + Fse)$, and VMS severity score for a specific week during the double-blind treatment period is defined as $(1xFmi + 2xFmo + 3xFse)/(Fmi + Fmo + Fse)$ where Fmi, Fmo, and Fse are the daily frequencies of mild, moderate, and severe VMS, respectively, during each applicable study week.

Co-primary endpoints will be evaluated at Week 4 and Week 12. See Section 10.3 for definition of baseline.

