10.3.2 Data handling

There will be no imputation of the missing data for the primary analysis. The details of the missing data handling for sensitivity analysis will be provided in the SAP.

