#### **5.4.2 Definition of the average daily severity score of mild to severe VMS**

The daily VMS severity score is defined as  $(2xFmo + 3xFse)/(Fmo + Fse)$  for any day before the first dose day, and  $(1xFmi + 2xFmo + 3xFse)/(Fmi + Fmo + Fse)$  for any day on or after the first dose day, where Fmi, Fmo, and Fse are the daily frequencies of mild, moderate, and severe VMS, respectively. It will be rounded off the third decimal place and reported the value to the second decimal place.

The average daily VMS severity of mild to severe VMS at a time point (Baseline, Week 1, 2, 3, 4, ..., 12) is the average of the daily severity of available diary days in the corresponding 7-day window defined in Table 4.

A daily severity score of zero (0) is assigned if it is reported that no VMS occurred on that day. VMS data on the day of Week 12 visit is not used for the calculation of average daily VMS severity. If the count of available VMS data in a specific week is less than four (4), latest diaries in the previous window can be carried as needed to make 4 diaries available in this window. Then the average daily VMS severity in the week is calculated.

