#### 7.9.1.1 Efficacy Analysis for Co-Primary Efficacy Endpoints

Change from baseline to Week 4 and Week 12 in the average daily frequency of moderate to severe VMS will be analyzed using repeated measures ANCOVA model with an unstructured covariance structure. The analysis model will include baseline value of the endpoint as a covariate and visits, treatment, interaction between visit and treatment, interaction between baseline and visit, antidepressant using (Y,N) , and interaction between antidepressant using (Y,N) and treatment as fixed effect. Baseline, weeks 1, 2, 3, 4, ..., 12 will be used for this analysis. (Table 14.2.1.1.A)

Similar analyses will be conducted for VMS severity score. (Table 14.2.1.2.A). The primary efficacy analysis will also be performed using PP population. (Table 14.2.1.1.B, Table 14.2.1.2.B)

If the normality assumption for the model is not met, the non-parametric method ranked ANOVA will be performed.

The scatter Plot of Mean change from baseline in VMS frequency and severity by treatment will be generated. (Figure 14.2.3.1, Figure 14.2.3.2). The scatter Plot of observed mean values of VMS frequency and severity by treatment will be generated. (Figure 14.2.4.1, Figure 14.2.4.2). The bar graph of Mean change from baseline in VMS frequency and severity at Weeks 4 and 12 by treatment will be generated. (Figure 14.2.5.1, Figure 14.2.5.2) The box plot of change from baseline in VMS frequency and severity by treatment will be generated as well. (Figure 14.2.6.1, Figure 14.2.6.2)

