#### 7.9.4 Sensitivity Analysis of Efficacy Endpoints

Sensitivity analyses for Efficacy Endpoints as following.

The sensitivity analysis will be conducted using primary analysis model with applicable covariates for ITT subjects without using antidepressants. (Table 14.2.2.1.A, Table 14.2.2.1.B, Table 14.2.2.2.A, Table 14.2.2.2.B)

The primary endpoints will also be analyzed using an ANCOVA model at week 4 and 12. The analysis model will include baseline value of the endpoint as a covariate and treatment as fixed effect. (Table 14.2.3.1, Table 14.2.3.2)

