### 7.12.2 Data Handling of Dropouts or Missing

Missing data will not be imputed in the summary at each time point. The missing data will not be imputed for efficacy analyses. For AE start and/or end date missing or partial missing, the AE will be treated as TEAE if it cannot be determined a non-TEAE.

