**8. CHANGES FROM THE PROTOCOL**

Subgroup analysis of antidepressant using (Y, N) will not be performed because there are not enough subjects with using antidepressant for the analysis.

Analysis for PP Population does not apply to secondary endpoints. These analyzes were considered to be excessive.

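### The SAP fills sparse diary weeks from the previous week for both co-primary endpoints, although the protocol and the SAP both say missing efficacy data are not imputed

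*SAP*

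**What the plan says.** Protocol 2.2.1 gives average daily frequency as "defined as the sum of the number of moderate to severe VMS during 1 week divided by the number of days with data". It sets no minimum number of days, does not borrow from other weeks, and leaves details to the SAP. Protocol 10.3.2 adds: "There will be no imputation of the missing data for the primary analysis". SAP 7.12.2 agrees: "The missing data will not be imputed for efficacy analyses".

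The derivation in SAP 5.4.1 (text under Table 4) differs. When a week holds fewer than four diaries, "the latest diaries in the previous window can be carried as needed to make 4 diaries available in this window", and the average is then taken. SAP 5.4.2 repeats this for severity: "latest diaries in the previous window can be carried as needed to make 4 diaries available in this window".

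The derived weekly values go straight into the main model. SAP 7.9.1.1 states: "Baseline, weeks 1, 2, 3, 4, ..., 12 will be used for this analysis".

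SAP section 8 lists two departures from the protocol. One drops the antidepressant subgroup; the other is "Analysis for PP Population does not apply to secondary endpoints". The carry rule is not there. Of the two sensitivity analyses in SAP 7.9.4, one restricts the population to subjects not using antidepressants. The other changes the model: "The primary endpoints will also be analyzed using an ANCOVA model at week 4 and 12". Neither changes how the weekly values are derived.

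**The concern.** The documents describe the co-primary endpoints in two incompatible ways. Under the protocol, a week without diaries is missing and the repeated measures model handles it. Under SAP 5.4.1 and 5.4.2, it can be filled from the week before, and the model then treats it as observed. Responder status, which is built on the same weekly frequency, inherits the filled value.

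The rule also leaves four cases open:

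- **Week 1.** The preceding window in Table 4 is Baseline (Day -7 to -1), and no exemption is stated. Pre-dose days could count as Week 1, which enters the model and time to response. Read literally, they could even supply the post-baseline value that ITT membership requires in SAP 4.3.
- **Chaining.** Nothing says whether a filled window may feed the next one.
- **Shortfall.** Nothing says what happens when the preceding window cannot supply enough diaries.
- **Discretion.** The wording permits carrying but does not require it.

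Two programmers could derive different co-primary datasets from this text.

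**Working it through.** The plan states no figure to reproduce here. The check is a count of diary days, followed by illustrations on stated assumptions.

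**1. Carried share of a weekly value.** With k own diaries (k < 4), the weekly value is [k × current mean + (4 − k) × carried mean] / 4, so the carried share is (4 − k)/4: 25% for k = 3, 50% for 2, 75% for 1, 100% for 0.

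**2. The two co-primary time points.** Table 4 sets Week 3 as Days 16–22, Week 4 as Days 23–29, Week 11 as Days 72–78, and Week 12 as starting on Day 79. For a subject with complete diaries up to her last diary day, using a single-step carry:

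| Last diary, Week 4 case | Last diary, Week 12 case | Own diaries | Carried share |
|---|---|---|---|
| Day 16–18 | Day 72–74 | 0 | Only 1–3 donor days; four cannot be reached and the rule is silent |
| Day 19–22 | Day 75–78 | 0 | 100% |
| Day 23 | Day 79 | 1 | 75% |
| Day 24 | Day 80 | 2 | 50% |
| Day 25 | Day 81 | 3 | 25% |

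**3. Week 1.** Assume a baseline of 10 VMS/day and a true Week 1 rate of 5/day. The change of −5 becomes −3.75, −2.5, −1.25 or 0 with 3, 2, 1 or 0 own diaries. Severity has a further problem, because SAP 5.4.2 omits mild VMS before the first dose. For an assumed day with 3 mild, 5 moderate and 2 severe events, the pre-dose formula gives (2×5 + 3×2)/7 = 2.29 and the post-dose formula gives (3 + 2×5 + 3×2)/10 = 1.90. A carried baseline day therefore brings a different score definition with it.

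**4. Week 12 window.** SAP 5.4.1 speaks of a 7-day window, but Table 4 gives Week 12 ten days (79 to 88) and excludes the visit day. The visit may fall on Day 85 ± 3, and Protocol 5.2.3.5 collects the diary at that visit. If diaries stop there, own diaries number (visit day − 79): 3, 4, 5, 6, 7, 8, 9 for visits on Days 82 to 88. A Day 82 visit leaves three (Days 79–81), so the rule fires in a fully compliant subject and adds Day 78.

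**5. How often the rule fires.** Assume independent daily completion with probability p. The chance of fewer than four diaries is P(X ≤ 3), X ~ Binomial(n, p), with n = 7 for an ordinary week and n = 3 to 9 for Week 12.

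| n | 3 | 4 | 5 | 6 | 7 | 8 | 9 |
|---|---|---|---|---|---|---|---|
| p = 0.9 | 1.000 | 0.344 | 0.081 | 0.016 | 0.003 | 0.000 | 0.000 |
| p = 0.8 | 1.000 | 0.590 | 0.263 | 0.099 | 0.033 | 0.010 | 0.003 |

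At 90% completion, 0.3% of ordinary weeks trigger the carry. For completers' Week 12 windows it is 21% with visits uniform over Days 82–88, or 11% with visits centred on Day 85 (weights .05, .10, .20, .30, .20, .10, .05). At 80% completion the figures are 3.3% against 29% and 20%. These count triggers, not bias.

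**6. Bias, illustration only.** Daily diaries were simulated (3000 per arm, 40 replicates, Monte Carlo SE at most 0.0015) with dropouts' last diary uniform over Days 1–81, effect time constants of 14 and 30 days, and a Week 12 difference of about −1.85 VMS/day. The model was unstructured repeated measures with baseline-by-visit and treatment-by-visit terms; the antidepressant terms were omitted. Single-step carry was compared with the mean of available days:

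| Dropout, placebo / active | Shift in the Week 4 and 12 difference |
|---|---|
| 15% / 15% | 0.8–1.1% toward zero |
| 10% / 25% | 2.8–3.6% toward zero |
| 25% / 10% | 1.1–1.3% away from zero |

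Carrying Baseline into Week 1 accounts for at most 0.006 VMS/day of this.

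**The case against.** The best defence is that this is a derivation rule and not imputation. Protocol 2.2.1 and 10.3.1 delegate endpoint detail and data handling to the SAP, the rule sits among the derived variables, and SAP 7.12.2 could be read as governing weekly values once derived. On that reading only a cross-reference is missing. The argument has some force for a week with three own diaries. It fails for a week with none, where the whole value comes from another week. It also conflicts with the protocol's definition, which confines the average to days with data in that week.

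The practical effect is probably small, and that point stands. With 15% dropout spread evenly over Days 1–81, a wholly carried Week 12 value arises in 15% × 4/81 = 0.7% of subjects, or about 0.7 of 91 per arm; at 25% dropout it is about 1.1. Off-treatment subjects are kept on study, and site calls should reduce diary gaps. The trigger rates and simulated shifts rest on assumptions, and the baseline-to-Week 1 reading is a literal one.

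The blinded data review (SAP 7.1) may add handling rules before lock. That is a route to closing the open cases, but it does not itself close them. The SAP's table list is not in the public text, so an analysis without the carry cannot be wholly excluded; the SAP text available describes none.

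One could also keep the carry and declare it as an exception. That would end the contradiction, but the primary analysis would still contain imputed weeks the protocol said it would not have.

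**Conclusion.** The concern holds and should be fixed. The rule covers both co-primary endpoints, contradicts the no-imputation statements in Protocol 10.3.2 and SAP 7.12.2, and is missing from SAP section 8. The carried shares, the affected last-diary days and the Day 82 count follow from Table 4 and the visit window, given a single-step carry and diaries that stop at the visit. The size and direction of bias depend on dropout by arm and cannot be obtained from the documents. On a single-step reading it is likely small. Chaining, which the text does not exclude, was not simulated and could fill more: with no diaries after Week 3, all nine weeks from Week 4 to Week 12 would be filled. The case rests on conflicting and incomplete derivations of the co-primary endpoints, not on a demonstrated large bias.

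**What to change.** - Remove the carry from the primary derivation in SAP 5.4.1 and 5.4.2, and average the available days within each Table 4 window.
- Set a week with no diaries to missing and leave it to the repeated measures model. If a minimum number of days is wanted, fix it before unblinding and list it in section 8, because the protocol has none.
- State that pre-dose diaries never count toward a post-baseline week or toward ITT membership.
- For Week 12, use available days from Day 79 to the day before the visit (to Day 88 if there is no visit), without borrowing from Week 11. Correct the 7-day wording, and list the variable window length in section 8, since the protocol also describes a 7-day period.
- If the carry is kept, make it a labelled sensitivity analysis, single-step only and never from Baseline.

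The cost is SAP wording and derivation code. The downside is that a few weekly values become missing or rest on fewer days, for example three for a Day 82 visit.
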